The design for this project will be a Randomized Control Trial (RCT), combined with Time-series (TS; Borckardt et al, 2008). Participants will be randomized at an individual level to either BA + Treatment as Usual (TAU) or TAU. Block randomization, using tables with random numbers with blocks of four, will be used in order to minimize the confounding effect of changes in general care over time. Randomization will be stratified according to site (i.e. Lund, Malmö, Kristianstad, Helsingborg). Random number tables will be generated in SPSS. The data will be handled with Intention to treat (ITT) analysis, so that once participants are randomized, their data will be included in all analyses regardless of whether they drop-out of the study prior to its termination.

Every participant receives a consecutive research number indicating to which site they belong (Lund – L01-..., Malmö – M01 - ...; Kristianstad – K01-..., Helsingborg – H01-...). The researcher who is methodologically responsible prepares the randomization lists in four series

(one per site). The randomization numbers are named according to strata (Lund – LR01-..., Malmö – MR01 - ...; Kristianstad – KR01-..., Helsingborg – HR01-...). From the lists, a research nurse prepares four series of consecutively numbered, sealed, opaque envelopes, each containing information on which group the participant is randomized to. After inclusion in the study, the research participant is given the envelope to open. After reading, PI handles a letter containing information on which upcoming procedures for the group to which the participant has been randomized. The randomization enveloped is handled back to PI and stored in a locker, together with the master key.

In the master key, PI register the name of the participant in combination with the research code and the randomization code. Data from forms are collected online, encoded by the research number, and stored on Lund University server. These assessments will be blinded to researchers analyzing the data. Videos and audio-recordings will be stored on USB in a locker separate from the master key. Recordings will only be reviewed on computers not connected to Internet.

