All participants randomized to the intervention during the pilot phase as well as the 10% of the individuals with the highest number of days admitted to hospital 12 months before baseline, will be selected for Time-Series Design (TS). The TS will follow an A-B replication case-series design where the number of days of GA to hospital will be monitored monthly, retrospectively with data from the local hospital records, from one year ahead of assigning to the study (A) and during the time the participant is allocated to either BA+TAU or TAU (one year; B).

Testing Schedule

For a visual description of the testing schedule, please see Figure 1, Bilaga 2c.

1. Individuals with symptoms suggesting that they may fulfill inclusion criteria, are asked by any clinician at the current department, if they want to participate in the study. If the individual is interested in participating, the clinician passes contact information to the PI.
2. PI checks if the inclusion criteria seem to be fulfilled and no exclusion criteria.
3. PI provides written and verbal information about the study, including time for questions and asks the individual to sign the consent form.
4. PI registers the participant in the screening log and provides a consecutive research number.
5. PI performs assessments with:
 - a. M.I.N.I. 7.0.0 (Sheehan, Lecriubier, Harnett-Sheehan, Janavs, Weiller, Bonara, Kesker, Schinka, Knapp, Sheehan & Dunbar, 1997; Lecriubier, Sheehan, Weiller, Amorim, Bonara, Sheehan, Janavs & Dunbar, 1997)
 - b. SCID II (First, Gibbon, Spitzer, Williams & Benjamin, 1998)
 - c. Fem frågor (Holmqvist & Nylander, 2013a),
 - d. AUDIT (Saunders, Aasland, Babor, Delafuente, Grant, 1993; Babor, Higgins-Biddle, Saunders & Monteiro, 2001)
 - e. DUDIT (Berman, Bergman, Palmstierna & Schlyter, 2005).
6. PI provides a consecutively numbered randomization envelope which the participant opens and signs. This is registered in the randomization log. According to which

group the participant is enrolled in, a sheet providing information on the study is given and explained.

7. Data collection at baseline by PI:
 - a. For the individuals randomized to the control group, data from hospital records for the previous 12 months, and CGI-S (Guy, 1976), are recorded with baseline date on the day for the randomization.

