 - Outcome is data from IES and the CES (Liljedahl, Helleman, Daukantaite & Westling, 2017) completed by the participants and clinicians administering BA after pilot testing, 6 and 12 months
8. Can the *Five Self-Harm Behaviour Groupings Measure* (5S-HM: Liljedahl & Westling, 2014) reliably and validly measure behaviors ranging from indirect to direct self-harm and attempted suicide, with varying degree of frequency and severity?
 - Outcome is data from questionnaire 5S-HM (Liljedahl & Westling, 2014), ISAS (Klonsky & Glenn, 2009; Glenn & Klonsky, 2011); Swedish version of the ISAS (Lindholm, Bjärehed & Lundh, 2011) and DERS (Gratz & Roemer, 2004); Swedish version of the DERS (Friberg, 2006).

Required sample size and a priori power analyses

G*Power, 3. 1. 7 (Faul, Erdfelder, Lang, & Buchner, 2007) was used to calculate a priori power for analyzing main effects and interaction for an A X B mixed design where A is a between-subject factor with two levels (experimental and control groups) and B is a within-subjects factor with three levels (three repeated assessments). The main statistical analyses will be either mixed (within-between) Analysis of Variance (ANOVA) or Analysis of Covariance (ANCOVA), controlling for baseline. Simpler univariate analyses will be calculated, but the power analyses summarized here are for the ANOVA model.

Assuming that three effects (i.e., between levels of the factor A, within levels of the factor B and within-between interaction A X B), are of medium size ($f = 0.25$; see Cohen, 1988), a significance level is of $\alpha = .05$, and the power values of the F tests are .85, a total of $N = 98$ per treatment site must be recruited ($n=196$ including both Stockholm and Lund, whose data will be grouped and analyzed separately).

Attrition in this population based on previous studies has been estimated to be approximately 25% (Stoffers, Völlm, Rucker, Timmer, Huband & Lieb, 2012; Nadort, Arntz, Smit, Giesen-Bloo, Eikelenboom, Spirnhoven, van Asselt, Wensing, & van Dyck., 2009). In order to attain the required sample size for these power estimates, including expected attrition, a total of $N= 124$ participants is required, with $n=62$ participants in each group (treatment and control).

Significance:

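### Fixed, published blocks of four within each site give the enrolling PI an opportunity to deduce up to about a third of allocations, and the plan commits to no baseline adjustment

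*Combined protocol and SAP*

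**What the plan says.** The Study design section of the combined protocol and SAP describes a two-arm trial randomized by individual: "Block randomization, using tables with random numbers with blocks of four", stratified by site (Lund, Malmö, Kristianstad, Helsingborg). On preparation it says: "The researcher who is methodologically responsible prepares the randomization lists in four series". A research nurse then fills a separate numbered series of sealed, opaque envelopes for each site.

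Under Testing Schedule, step 2 reads "PI checks if the inclusion criteria seem to be fulfilled and no exclusion criteria". The PI also takes consent (step 3) and carries out the diagnostic assessments (step 5). Step 6 reads "PI provides a consecutively numbered randomization envelope which the participant opens and signs". Study design adds that the opened envelope goes back to the PI for storage, and: "In the master key, PI register the name of the participant in combination with the research code and the randomization code".

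The only people described as blinded are the researchers who analyze the data. The document mentions no varying block size, no withholding of the block size from the PI and no central allocation.

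The sample-size section plans 62 participants per group, 124 in all. It names the main analysis as either a mixed ANOVA or an ANCOVA that controls for baseline, without choosing.

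**The concern.** A sealed envelope conceals its own contents. It does not conceal what follows from the envelopes opened before it. When the block size is fixed, small and printed in the protocol, anyone who knows the earlier allocations at a site can work out some later ones. Here the PI holds all three pieces needed: the block size, the envelope number and every earlier result. The PI also judges eligibility and controls when the envelope is given.

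The main outcome comes from hospital records, which helps protect how it is measured. Record-based measurement and intention-to-treat analysis do not protect who enters an arm, or when. Entry requires at least 7 inpatient days or 3 emergency visits in six months, so prior use is substantial and probably varies. If it predicts later general-admission days, which is plausible but not shown in the documents, steering heavy users toward or away from one arm would shift the primary comparison. An unadjusted ANOVA, which the plan leaves open, would carry that shift into the follow-up between-group difference.

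**Working it through.** **Inputs.** Block size 4, four site lists, two arms (Study design). Planned total 124, 62 per arm (sample-size section). The 1:1 ratio, hence two and two in each block, is inferred from the equal group sizes.

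**The plan's own figures.** The document gives no figure for predictability. Its 98 before attrition reproduces for the between-group effect. With f = 0.25, m = 3 assessments and an assumed correlation of 0.5 (not stated), λ = f²·N·m / (1 + (m − 1)ρ) = 0.0625 × 98 × 3 / 2 = 9.19, which gives power 0.851 at α = 0.05. Then 98 × 1.25 = 122.5, or 124 for equal arms. Only the 124 is used below.

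**Allocations deducible with certainty.** A block has six equally likely orders: AABB, ABAB, ABBA, BAAB, BABA, BBAA. An allocation is known once one arm has used both its places.
- Places 1 and 2: never known.
- Place 3: known in 2 of 6 orders (AABB, BBAA).
- Place 4: always known.
- Expected per block: 1/3 + 1 = 4/3, so (4/3)/4 = 8/24 = 33.3%.
- Complete blocks, 124 participants: 124/3 = 41.3.
- With 31 per site (seven full blocks plus three places): 4 × (7 × 4/3 + 1/3) = 38.7, or 31.2%. Over all ways of dividing 124 among four sites, the share runs from 31.2% to 33.3%.

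**Best guess.** The chance of being right is 1/2 at place 1, 2/3 at place 2, (1/3 × 1 + 2/3 × 1/2) = 2/3 at place 3, and 1 at place 4. The mean is 2.833/4 = 17/24 = 70.8%. With 31 per site it is (7 × 2.833 + 1.833)/31 = 69.9%.

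**Possible size of imbalance (assumption, not in the documents).** Suppose entrants steered toward one arm differ at baseline by 0.25–0.5 SD from those steered toward the other.
- Using only the certain places: one third of that, 0.08–0.17 SD.
- Acting on every best guess: (2 × 0.708 − 1) = 0.417 of it, 0.10–0.21 SD.

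**Effect of varying the block size.** Simulation with 31 per site and an observer who knows the possible sizes but not their order:

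| Block sizes | Known with certainty | Best guess right |
|---|---|---|
| 4 only | 31.2% | 69.9% |
| 2, 4, 6 | 3.9% | 69.5% |
| 4, 6, 8 | 2.0% | 67.2% |

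**The case against.** Several safeguards deserve credit. Lists and envelopes are prepared by people other than the role described as enrolling. Candidates are first approached by any clinician in the department, so the PI does not choose who is referred. Consent, a screening-log entry, a consecutive research number and five assessments all precede the envelope, so a selective exclusion after registration would leave a trace. Much of eligibility is countable: inpatient days, emergency visits, age. ANCOVA with baseline control is already one of the two named analyses, and twelve months of prior hospital data are collected.

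These points stand, and they narrow the room for steering. What remains is mainly the timing of entry and the judgement at step 2, where the criteria need only appear to be met.

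A reader might infer that the PI actually knew a third of the allocations, or that enrolment was steered. The documents do not support either. Deduction requires following each site's sequence and block boundaries, and nothing shows that this was done. The documents also do not say whether the PI is one person or one per site; the arithmetic within a site is the same either way. A reader might also infer that varying the block size closes the gap. The table shows that it removes nearly all certainty but little of the guessing.

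**Conclusion.** The concern holds as an opportunity for prediction: up to 31–33% of allocations (about 39–41 of 124) deducible with certainty, and best guesses right about 70% of the time. This rests on 1:1 blocks, on a PI who knows the printed block size and follows each site's sequence, and on a total of 124. With another total the count changes, while the share stays near one third. Bias in the comparison of general-admission days is possible, not demonstrated. Its size cannot be derived from the documents, and the SD figures above are illustrations.

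Timing affects the remedy. This version is dated April 2018. The Pilot phase section starts active data collection in March 2016 and ends it 36 months later, about March 2019. If that end includes the 12-month follow-up, enrolment would have had to close around March 2018, so few or no envelopes may be left. The analysis-stage changes therefore matter most.

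**What to change.** 1. Commit to ANCOVA for the primary analysis, with baseline general-admission days as covariate, instead of leaving ANOVA or ANCOVA open. Count those days back from the randomization date in both arms: Testing Schedule step 7 dates baseline at randomization for controls but at the contract for the intervention group. Adjustment reduces bias through prior hospital use. It cannot remove selection on unmeasured factors.
2. Add a sensitivity analysis. For each participant, compute the probability of assignment to BA given the earlier allocations in the block (0, 1/3, 1/2, 2/3 or 1) and relate baseline general-admission days to it. Without steering there should be no association. Report the estimate with its confidence interval, since a non-significant result would not rule steering out.
3. For any part of a site list still unused, regenerate it with randomly varying block sizes (for example 4, 6 and 8) that are not disclosed to the enrolling PI. Residual guessing would remain unless the PI's role in enrolment or knowledge of past allocations also changed.

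The cost is small: one regeneration of any remaining lists and envelopes, and a little more analysis using the randomization log and hospital data already collected. Imbalance within a site could be slightly larger: at most 4 within a block of eight, against 2 within a block of four.

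### Randomization is stratified by four sites but the stated ANOVA/ANCOVA has no site term; if site is prognostic, the between-group test is conservative and forgoes a little power

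*Combined protocol and SAP*

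**What the plan says.** Under Study design, the combined protocol and SAP sets the allocation: "Block randomization, using tables with random numbers with blocks of four", and "Randomization will be stratified according to site (i.e. Lund, Malmö, Kristianstad, Helsingborg". Each of the four sites has its own randomization list and envelope series.

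Under Required sample size and a priori power analyses it sets the analysis: "The main statistical analyses will be either mixed (within-between) Analysis of Variance (ANOVA) or Analysis of Covariance (ANCOVA), controlling for baseline". In the power model, "A is a between-subject factor with two levels (experimental and control groups" and "B is a within-subjects factor with three levels (three repeated assessments". Baseline is the only covariate named. Simpler univariate analyses are also announced, without covariates.

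Site is not named as a factor or covariate anywhere, and it is not expressly excluded. The one sentence that links site to analysis says that data from Stockholm and Lund will be analyzed separately. Those two places are not the four randomization strata.

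**The concern.** Blocking within site keeps the arms close to balanced at each site, so differences between sites largely cancel out of the treatment contrast. A model without site leaves the same differences in its residual error. The reported standard error then exceeds the true one, p-values are too large and confidence intervals too wide.

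This happens only if site is related to the outcome. That is plausible here. The primary question is answered from medical records, including days of general admission, and the Sites section describes four geographic divisions with four inpatient settings. At stake is some efficiency, and a choice between adjusted and unadjusted results that stays open until the data are seen.

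**Working it through.** **Inputs from the documents:** four strata, blocks of four, two arms, m = 3 assessments, f = 0.25, alpha .05, power .85, N = 98 before attrition (49 per arm).

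**Assumptions, because the documents give no value:** correlation rho = 0.5 between assessments; r, the share of the variance of the subject mean that lies between sites, tried from 0 to .20.

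**1. The plan's own figure.** For the between-group test, lambda = N f² m / (1 + (m − 1) rho) = 98 × 0.0625 × 3 / 2 = 9.19. With 1 and 96 degrees of freedom the noncentral F gives power .851, so 98 reproduces. The result depends on rho: 80 at 0.3 and 118 at 0.7. Under the same settings the within and interaction tests need only 32. The stated 98 therefore rests on the between-group test, which is the one exposed to site variance.

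**2. Standardized effect.** d = 2f = 0.5. The SD of the subject mean is sqrt((1 + 2 × 0.5)/3) = 0.816. SE = 0.816 × sqrt(2/49) = 0.165, so delta = 0.5/0.165 = 3.03. The normal approximation gives power .858 at r = 0, slightly above the exact .851.

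**3. Leaving site out of a between-group test without baseline.**

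- Model SE / true SE = 1/sqrt(1 − r)
- Actual alpha = 2 Phi(−1.96/sqrt(1 − r))
- Power without site = Phi((delta − 1.96)/sqrt(1 − r))
- Power with site = Phi(delta/sqrt(1 − r) − 1.96)

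For r = .10, sqrt(.90) = 0.949. The SE ratio is 1.054. Power without site is Phi(1.071/0.949) = Phi(1.129) = .871. Power with site is Phi(3.031/0.949 − 1.96) = Phi(1.235) = .892.

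| r (assumed) | SE too large by | Actual alpha | Power without site | Power with site | Points forgone |
|---|---|---|---|---|---|
| 0 | 0% | .050 | .858 | .858 | 0 |
| .01 | 0.5% | .049 | .859 | .861 | 0.2 |
| .05 | 2.6% | .044 | .864 | .875 | 1.1 |
| .10 | 5.4% | .039 | .871 | .892 | 2.1 |
| .20 | 11.8% | .028 | .884 | .924 | 3.9 |

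A simulation (four sites, blocks of four, N = 98, 6000 runs per scenario) agrees. At r = .05, .10 and .20, power without and with site was .860 and .868, .866 and .889, .870 and .915.

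**4. ANCOVA with baseline.** Two simulations, power without site → with site:

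| Site share | N = 98, 6000 runs | N = 96, 4000 runs |
|---|---|---|
| .05 | .931 → .934 | .935 → .938 |
| .10 | .934 → .939 | .931 → .938 |
| .20 | .943 → .950 | .938 → .953 |

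The gains run from 0.2 to 0.8 points in the first and from 0.3 to 1.5 in the second. Baseline already carries much of a stable site difference.

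**5. Group-by-time.** A constant site effect cancels from the within-subject error. Simulating the change from baseline to follow-up (N = 96, 4000 runs, correlation .5) gave power without and with site of .805 and .804, .802 and .801, .796 and .795 for shares of .05, .10 and .20. Type I error was about .045 to .052 both ways.

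**The case against.** The strongest reply has three parts.

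First, the two-factor description belongs to the power calculation, and naming a family of models does not rule out further terms. It is true that nothing excludes site. But the stated main analysis names baseline and nothing else, and the Stockholm and Lund sentence gives no rule for the four strata. An analyst who follows the text fits a model without site.

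Second, the effect is conditional. The documents give no between-site variance, all four sites belong to one regional organization, and at r = .01 the standard error is only 0.5% too large. This stands, and it is why the sizes are given as a range under assumption.

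Third, assessments are at baseline, 6 and 12 months, so in the mixed ANOVA a treatment effect appears mainly as group-by-time, where a constant site effect does no harm. In the ANCOVA, baseline does most of the work. This also stands, and it rules out applying the larger figures to every test. It does not dispose of the point. The plan leaves ANOVA or ANCOVA open, the simpler analyses have no stated covariates, and N = 98 reproduces from the between-group test. The Study design section itself gives changes in general care over time as the reason for blocking. If such changes differ by site, neither the within-subject comparison nor baseline removes them.

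A reader might infer that the trial is underpowered or that its type I error is inflated. Neither follows. The effect size is set against a total SD that already contains any site variance, so calculated power without site stays at or above the planned .85 at every r tried. The error in alpha is in the safe direction.

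**Conclusion.** The point holds in a limited form. The trial stratifies by four sites, and the stated model does not include them. If site is prognostic, a between-group test without baseline has a standard error about 3%, 5% or 12% too large and forgoes about 1, 2 or 4 power points compared with a site-adjusted test, for assumed site shares of 5%, 10% and 20% and an assumed correlation of 0.5. With baseline in an ANCOVA the forgone gain is about 1 point. For group-by-time it is nil if site effects are constant. If site explains nothing, nothing is lost.

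This is an inexpensive gain in efficiency, not a threat to validity. It does not bear on whether the recruitment target of 124 leaves enough participants after attrition, which is a separate question.

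**What to change.** In the section on sample size and power, where the main analysis is named, state that the four-level site stratum (Lund, Malmö, Kristianstad, Helsingborg) enters as a fixed factor, next to baseline, in the ANCOVA and in the between-group comparisons. For the mixed ANOVA, add a site-by-time term if site differences may change over time, because a site main effect alone does nothing for the group-by-time test. In the same edit, reconcile the Stockholm and Lund sentence with the four strata.

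The cost is a sentence or two and three degrees of freedom (96 − 3 = 93 for the between-group error at N = 98). Site-by-time takes a further (4 − 1) × (3 − 1) = 6 from the within-subject error. No new data are needed, since every research number already carries the site code.

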 - b. For individuals randomized to the intervention group data from hospital records and CGI-S (Guy, 1976), are recorded with baseline date on the day for the contract (i.e. day when BA is accessible).
8. Data collection at baseline by a Research Assistant (RA):
 - a. After randomization PI contacts a local RA who schedules an appointment with all participants, and administers a link to the self-administered forms:
 - i. 5S-HM (Liljedahl & Westling, 2014),
 - ii. WHODAS 2.0 (WHODAS 2.0; 2014),
 - iii. Brief COPE (Carver, 1997; Muñoz & Torkelson, 2005), DERS (Gratz & Roemer, 2004; Friberg, 2006),
 - iv. ISAS (Klonsky & Glenn, 2009; Glenn & Klonsky, 2011; Lindholm, Bjärehed & Lundh, 2011).
 - b. RA is available for the individual and provides help if necessary, when completing the forms online.
 - c. For individuals randomized to the intervention group RA further contacts their primary clinician as well as ward staff at the ward providing BA, to schedule an appointment for negotiation resulting in a BA contract. At the end of the negotiation IES and CES (negotiation part) are completed online.
9. Data collection at 6 and 12 months (± 2 weeks) is repeated as baseline, with the change that the contract negotiation is replaced by contract evaluation for the intervention group and data from hospital records is collected from the previous 6 months.

Pilot phase

The first three months of the study (Sept, 2015 – Jan, 2016) will form a pilot phase with the goal of optimizing the intervention, evaluate the inclusion and exclusion criteria and preliminary testing to determine whether the quality and quantity of assessments are adequate and feasible. At the termination of the pilot phase evaluation with IES and CES (Liljedahl, Helleman, Daukantaite & Westling, 2017) will be performed.

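### For the questionnaire and CGI-S outcomes, the named ANOVA or ANCOVA does not keep every randomized participant in the analysis as promised; at 25% attrition about 31 of 124 would fall out of the ANOVA

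*Combined protocol and SAP*

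**What the plan says.** The Study design section commits to intention to treat: "once participants are randomized, their data will be included in all analyses regardless of whether they drop-out of the study prior to its termination".

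The section on required sample size and power names the method: "The main statistical analyses will be either mixed (within-between) Analysis of Variance (ANOVA) or Analysis of Covariance (ANCOVA), controlling for baseline". In the design that was powered, "B is a within-subjects factor with three levels (three repeated assessments". Under Testing Schedule, item 9, these are baseline and two follow-ups: "Data collection at 6 and 12 months (± 2 weeks) is repeated as baseline".

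The sample-size section also says: "Attrition in this population based on previous studies has been estimated to be approximately 25"%. It raises the number to recruit to 124 (62 per group) on that account.

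The outcomes come from two kinds of source. The section linking methods to research objectives takes the primary outcome from medical records, and the section on hospital records has these collected retrospectively, month by month. Research questions 2 to 6 rest on questionnaires and CGI-S, which exist only if the participant is assessed.

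No section says how a missing assessment is handled.

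**The concern.** A classical within-between ANOVA works on complete rows. A participant with a baseline and a 6-month score but no 12-month score is removed, and the two observed scores go too. ANCOVA is less wasteful, because someone who misses only month 6 can stay in a 12-month ANCOVA, but anyone without the analysed follow-up value is still excluded. Applied as named, neither method gives the promised property for the attended outcomes. The attrition allowance points the same way: recruiting extra people to reach the required number makes sense only if those lost are expected to leave the analysis.

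What is at stake is the comparison behind research questions 2 to 6. If staying in the study is related to how a participant is doing, the completers in the two arms are no longer the groups that were randomized. There is also room to choose between ANOVA, ANCOVA and some missing-data rule after results are seen.

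**Working it through.** **Inputs from the plan (sample-size section).** f = 0.25, alpha 0.05, power 0.85, two groups, m = 3 assessments, 98 before attrition, 25% attrition, 124 recruited.

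**Assumption.** The plan gives no correlation ρ between assessments. I use 0.5, with 0.3 and 0.7 as a range.

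**Step 1: reproduce the plan's figure.** For the between-group effect, λ = N × f² × m / (1 + (m − 1)ρ), with F on 1 and N − 2 degrees of freedom.
- N = 98, ρ = 0.5: λ = 98 × 0.0625 × 3 / 2 = 9.19, power 0.851. The plan's 98 is reproduced. At ρ = 0.3 the requirement would be 80, and at 0.7 it would be 118.
- 98 × 1.25 = 122.5, rounded up to 123 and then to an even 124. The plan's 124 is reproduced.

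**Step 2: participants excluded.** 0.25 × 124 = 31, leaving 93. This counts attrition only; intermittently missed visits would add to it under the ANOVA. At other rates the loss is about 19 (15%), 25 (20%) or 37 (30%).

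**Step 3: power with 93 complete cases (between-group effect).**

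| ρ | λ | Power at N = 93 |
|---|---|---|
| 0.3 | 10.90 | 0.904 |
| 0.5 | 8.72 | 0.832 |
| 0.7 | 7.27 | 0.760 |

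For the group-by-time interaction at f = 0.25, power with 93 exceeds 0.99 at all three correlations.

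**Step 4: possible bias in a completer analysis.** All inputs here are assumptions: unit SDs, ρ = 0.5, true effect 0 at baseline and −0.50 at 6 and 12 months. Loss after 6 months follows a logistic model in the 6-month score, with an odds ratio of 2 or 3 per SD and the intercept set so that 25% are lost overall. Numerical integration gives:

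| Odds ratio | 6-month effect | Shrinkage | 12-month effect | Shrinkage |
|---|---|---|---|---|
| 2 | −0.464 | 0.036/0.50 = 7% | −0.482 | 0.018/0.50 = 4% |
| 3 | −0.428 | 0.072/0.50 = 14% | −0.464 | 0.036/0.50 = 7% |

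The 12-month shift is the 6-month shift times ρ. Rounding the 6-month effects to −0.46 and −0.43 first would give 8% and 14%. Completers also differ at baseline by 0.02 to 0.04 SD. In this scenario every 6-month score was observed, and the ANOVA discards those of the 31.

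**The case against.** **The primary outcome.** A reader might infer that the trial's primary analysis becomes a completer analysis. The documents do not support that. General admission is read from hospital records collected retrospectively, and someone who stops attending does not thereby lose those records. What remains is narrower: the plan does not say that extraction continues after drop-out, and Testing Schedule item 9 places it within the 6- and 12-month data collection.

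**Deletion is not stated.** A reader might infer that the plan orders incomplete cases deleted, or that its promise is impossible to keep. It does neither. Deletion follows from the named methods when nothing is added, and imputation before the ANOVA could satisfy the promise. The defect is that no such step is named.

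**ANCOVA.** It is an equal option in the plan. It keeps some participants whom the ANOVA loses, and a complete-case ANCOVA is valid when missingness depends only on the baseline covariate. This stands, but it does not put every randomized participant in the analysis.

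**Power.** With 93 rather than 98 the loss is about 2 points (0.851 to 0.832 at ρ = 0.5). It arises because 124 is 98 × 1.25 and not 98/0.75 = 131, which is a separate sample-size matter. A reader might also set 0.832 against the 0.923 obtained with N = 124. That figure needs 124 complete records, which no analysis method can supply for unanswered questionnaires.

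**Bias.** A reader might conclude that the randomized comparison is lost. The documents do not say that drop-out is related to severity, and the shrinkage under the assumed odds ratios is modest.

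**Conclusion.** The concern holds for the attended outcomes (WHODAS 2.0, Brief COPE, DERS, 5S-HM, ISAS, CGI-S). The intention-to-treat promise is not met by the mixed ANOVA or ANCOVA as named, because no missing-data method accompanies them. At the plan's own attrition rate about 31 of 124 would be excluded from the ANOVA.

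The count rests on the plan's figures. The power figure of 0.83 (0.76 to 0.90) rests on a correlation that the plan does not state; 0.5 is chosen because it reproduces 98. The shrinkage figures (about 7 to 14% at 6 months, 4 to 7% at 12) rest on assumed drop-out odds ratios and show what could happen, not what the documents predict.

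The point does not extend to the record-based primary outcome, beyond the need to state that records are followed after drop-out. It should be changed because a better method is cheap, although the likely numerical effect is moderate.

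**What to change.** **Attended outcomes.** Replace the mixed ANOVA with a likelihood-based linear mixed model that uses every available value. Put baseline, 6 and 12 months all in the outcome vector, with site, time and group-by-time as terms. With baseline as a covariate instead, anyone lost before 6 months would have no outcome row and be dropped again. Add a sensitivity analysis for data not missing at random.

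Two details need a sentence each:
- Under Testing Schedule item 8 the baseline questionnaires are completed after randomization. The plan should therefore say whether the arms are constrained to be equal at baseline (no group main effect) or a group term is added.
- A participant who leaves before giving any value cannot enter the model; report the number by arm.

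**Record-based primary outcome.** State that hospital records are extracted to 12 months for all randomized participants, including those who stop attending assessments where consent allows, and that all of them are analysed.

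**Cost.** This is a change of analysis wording, with no new visits or questionnaires and a model available in standard software. The downside is reliance on a missing-at-random assumption, which the sensitivity analysis is there to probe. The fix recovers partial data but not the power of 124 complete questionnaires.
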